### **Suppression of bleeding**

Suppression of bleeding is defined similarly to amenorrhea except that spotting is allowed. For each subject, achieving suppression of bleeding at the Final Month is defined as having 0 days of bleeding (spotting allowed) during the last 28 days prior to and including the last dose day with the interval starting at or beyond Study Day 11. The

suppression of bleeding analysis includes subjects with at least 38 days on study drug. If a subject does not have evaluable AH data during the last 28 days and no bleeding is indicated on UBQ ("Subject only had spotting that did not require the use of sanitary products" or "There was no visible blood on the sanitary products" is allowed), then the subject will be considered having achieved suppression of bleeding. The denominator will be the number of subjects with at least 38 days on study drug and having a suppression of bleeding status at the Final Month.

The number and percentage of subjects achieving suppression of bleeding at Final Month will be summarized by treatment group and compared between the elagolix treatment group and placebo using the Miettinen-Nurminen (M-N) method.

Time to suppression of bleeding is defined as the number of days from the first study drug dose date to the day a subject achieves suppression of bleeding (i.e., the day a subject achieves suppression of bleeding – the first study drug dose date + 1). For a subject who achieves suppression of bleeding, the day she achieves suppression of bleeding is defined as the next day of the last bleeding day during the Treatment Period. The median, Q1, and Q3 of time to suppression of bleeding will be calculated for subjects who achieve suppression of bleeding using Kaplan-Meier method.

Monthly analysis of bleeding for suppression of bleeding, incidence and cumulative incidence of suppression of bleeding will be provided in the same way as will be done for amenorrhea in [Table 1](#) and [Table 2](#). Plots will be provided by treatment group for percentage of subjects with incidence and cumulative incidence of suppression of bleeding during the Treatment Period, respectively.

In all the analysis for suppression of bleeding above, if the observed MBL volume over a window is 0 mL for a subject, then the subject is considered as no bleeding during that interval; if the observed MBL volume over a window is > 0 mL but there is no single daily observed AH data > 2 mL, the subject is also considered as no bleeding during that interval. Last bleeding day refers to the last day with observed AH data > 2 mL or the last day with UBQ indicating bleeding.

### **Hemoglobin Concentration**

Hemoglobin (Hgb) concentration data will be summarized as observed; missing data will not be imputed.

Baseline Hgb concentration is defined as the last measurement prior to or on the first dose date of study drug. The change and percent change from Baseline in Hgb concentration to each of Months 1 – 6 during the Treatment Period will be analyzed with one-way ANCOVA with treatment group as the main effect and Baseline as a covariate.

### **PGIC on Menstrual Bleeding Questionnaire**

For PGIC on menstrual bleeding (PGIC – MB), the number and percentage of subjects in each response category will be summarized at each applicable visit by treatment group. Missing data will not be imputed. No statistical tests will be performed.

For PGIC – MB, the response categories of "Very Much Improved" and "Much Improved" will be combined and the remaining five categories of the PGIC scale will be combined and labeled "Otherwise." The number and percentage of subjects with response of (a) "Very Much Improved" or "Much Improved," and (b) "Otherwise" will be summarized at each applicable visit by treatment group. Comparisons will be made using the Miettinen-Nurminen (M-N) method for each applicable visit in the Treatment Period.

### **Uterine Fibroid Symptoms Quality of Life (UFS-QoL)**

Improvement in quality of life will be assessed on the UFS-QoL Questionnaire (4-week recall). The change from Baseline to each applicable visit during the Treatment Period will be calculated and summarized by treatment group for each of the UFS QoL subscales (symptom severity, concern, activities, energy/mood, control, self-conscious, and sexual function) and the HRQL total. The change from Baseline to each applicable visit in the Treatment Period will be analyzed using ANCOVA with treatment as the main effect and corresponding Baseline UFS-QoL as a covariate to compare the elagolix treatment group

to placebo. Missing items within a subscale will be handled using the methods specified in the UFS QoL Scoring Manual. Missing data across visits will not be imputed.

## 8.5 Efficacy Subgroup Analyses

For the primary endpoint, the following subgroups will be explored to assess potential differences in treatment effect across subgroup levels.

- Baseline weight (< median, ≥ median)
- Baseline BMI (< median, ≥ median)
- Baseline BMI (< 25 kg/ m^2, 25 – < 30 kg/m^2, ≥ 30 kg/m^2)
- Ethnicity (Hispanic or Latino, Not Hispanic or Latino)
- Race (Black or African American, Not Black or African American)
- Baseline MBL volume (< median, ≥ median)
- Baseline FIGO classification as determined by TAU/TVU (0 – 3, 4, 5 – 8)
- Baseline uterine volume as determined by TAU/TVU (< median, ≥ median)
- Baseline primary fibroid volume as determined by TAU/TVU (< median, ≥ median)

Within each level of a subgroup variable, the proportions of responders, difference between proportions, and 95% CIs will be summarized within each subgroup level. No p-value will be provided for subgroup analysis. The data set after multiple imputation for the primary analysis as in Section 8.3.3 will be used for the subgroup analyses. For Baseline BMI, in case of small sample size at a subgroup level, the level of "< 25 kg/ m^2" and "25 – < 30 kg/m^2" may be collapsed.

## 9.0 Safety Analyses

### 9.1 General Considerations

Safety data will be summarized for the Safety Analysis Set. Safety summaries will be presented by treatment group. For the safety analysis, subjects are assigned to a treatment group based on the treatment actually received, regardless of the treatment randomized. If

a subject received more than one type of study drug, safety data will be analyzed in the treatment group to which she was randomized to. All safety analyses will be based on observed data. For analyses of safety endpoints, subjects who are missing an evaluation will not be included in the analysis of that particular parameter/visit, unless otherwise specified.

## **9.2 Adverse Events**

Adverse events (AEs) will be summarized and presented using primary MedDRA System Organ Classes (SOCs) and preferred terms (PTs) according to the version of the MedDRA coding dictionary used for the study at the time of database lock. The actual version of the MedDRA coding dictionary used will be noted in the AE tables and in the clinical study report. Specific adverse events will be counted once for each subject for calculating percentages, unless stated otherwise. In addition, if the same adverse event occurs multiple times within a subject, the highest severity and level of relationship to investigational product will be reported.

### **9.2.1 Treatment-Emergent Adverse Events**

Treatment-emergent AEs are defined as any AE with the onset that is after the first dose of study drug. AEs starting more than 30 days following discontinuation of study drug will not be included in summaries of treatment-emergent AEs. Events where the onset date is the same as the study drug start date are assumed to be treatment-emergent. All treatment-emergent AEs will be summarized overall, as well as by primary MedDRA SOC and PT. The SOCs will be presented in alphabetical order, and the PTs will be presented in alphabetical order within each SOC. The number and percentage of subjects experiencing treatment-emergent AEs will be summarized.

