An elective surgery/procedure scheduled to occur during a study will not be considered an AE if the surgery/procedure is being performed for a pre-existing condition and the surgery/procedure has been pre planned prior to study entry. However, if the pre-existing condition deteriorates unexpectedly during the study (e.g., surgery performed earlier than planned), then the deterioration of the condition for which the elective surgery/procedure is being done will be considered an AE.

If an AE, whether associated with study drug or not, meets any of the following criteria, it is to be reported to AbbVie clinical pharmacovigilance as an SAE within 24 hours of the site being made aware of the SAE (refer to Section 4.3 of the Operations Manual ([Appendix F](#)), for reporting details and contact information):

Death of Subject	An event that results in the death of a subject.
Life-Threatening	An event that, in the opinion of the investigator, would have resulted in immediate fatality if medical intervention had not been taken. This does not include an event that would have been fatal if it had occurred in a more severe form.
Hospitalization or Prolongation of Hospitalization	An event that results in an admission to the hospital for any length of time or prolongs the subject's hospital stay. This does not include an emergency room visit or admission to an outpatient facility.

Congenital Anomaly	An anomaly detected at or after birth, or any anomaly that results in fetal loss.
Persistent or Significant Disability/Incapacity	An event that results in a condition that substantially interferes with the activities of daily living of a study subject. Disability is not intended to include experiences of relatively minor medical significance such as headache, nausea, vomiting, diarrhea, influenza, and accidental trauma (e.g., sprained ankle).

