Important Medical Event Requiring Medical or Surgical Intervention to Prevent Serious Outcome	An important medical event that may not be immediately life-threatening or result in death or hospitalization, but based on medical judgment may jeopardize the subject and may require medical or surgical intervention to prevent any of the outcomes listed above (i.e., death of subject, life threatening, hospitalization, prolongation of hospitalization, congenital anomaly, or persistent or significant disability/incapacity). Additionally, any elective or spontaneous abortion or stillbirth is considered an important medical event. Examples of such events include allergic bronchospasm requiring intensive treatment in an emergency room or at home, blood dyscrasias or convulsions that do not result in inpatient hospitalization, or the development of drug dependency or drug abuse.

Serious adverse events and protocol-related nonserious AEs will be collected beginning when the subject signs the study-specific informed consent. From the time of study drug administration until PTFU Month 1 visit, all AEs, adverse events of special interest (AESIs), and SAEs will be collected whether solicited or spontaneously reported by the subject.

AbbVie will be responsible for suspected unexpected serious adverse reactions (SUSAR) reporting for the investigational medicinal product (IMP) in accordance with global and local requirements.

AEs will be monitored throughout the study to identify any of special interest that may indicate a trend or risk to subjects.

Adverse Events of Special Interest

The following AESIs will be monitored during the study:

- Bone fractures
- Mood and depression-related events
- Hepatic transaminase elevations

During the study, AbbVie may require additional information on AEs, SAEs, and/or AESIs to be collected and recorded in the eCRF.

Adverse Event Severity and Relationship to Study Drug

The investigator will use the following definitions to rate the severity of each AE:

Mild	The AE is transient and easily tolerated by the subject.
Moderate	The AE causes the subject discomfort and interrupts the subject's usual activities.
Severe	The AE causes considerable interference with the subject's usual activities and may be incapacitating or life threatening.

The investigator will use the following definitions to assess the relationship of the AE to the use of study drug:

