7.7 Sample Size Determination

Approximately 48 subjects will be randomly assigned (in a 2:1 ratio) to receive either elagolix 150 mg QD (N = 32) or placebo (N = 16). The sample size will provide at least 80% power to detect a difference between the elagolix 150 mg QD group and the placebo group in the percentage of subjects meeting the primary endpoint on MBL at the Final Month of the placebo-controlled Treatment Period, with a final volume < 80 mL and an improvement of $\geq 50\%$ from Baseline, assuming response rates of 10% for the placebo group and 55% for the elagolix 150 mg QD group with a 2-sided $\alpha = 0.05$. The above sample size was calculated using nQuery Advanced 8.1.

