4.2 Recording Data and Analyses of Safety Findings

AEs will be coded using the Medical Dictionary for Regulatory Activities (MedDRA). The number and percentage of subjects with treatment-emergent adverse events (TEAE) (i.e., any event that begins or worsens in severity after initiation of study drug through 30 days after the last dose of study drug) will be tabulated by primary MedDRA system organ class (SOC) and preferred term.

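### SAP 9.2.1 defines treatment-emergent AEs by onset alone, while Operations Manual 4.2 also counts worsening after first dose, so a pre-dose AE that worsens on drug may go uncounted

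*SAP*

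**What the plan says.** Operations Manual 4.2, which is part of the protocol as Appendix F, defines a treatment-emergent AE as "any event that begins or worsens in severity after initiation of study drug through 30 days after the last dose of study drug" and says that such events will be tabulated by system organ class and preferred term.

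SAP 9.2.1 specifies the same tabulation with a different rule: "Treatment-emergent AEs are defined as any AE with the onset that is after the first dose of study drug". It adds a rule for the first day, "Events where the onset date is the same as the study drug start date are assumed to be treatment-emergent", and an end to the window, "AEs starting more than 30 days following discontinuation of study drug will not be included in summaries of treatment-emergent AEs". It does not mention worsening.

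On what is recorded before dosing, Protocol 6.1 states: "Serious adverse events and protocol-related nonserious AEs will be collected beginning when the subject signs the study-specific informed consent". Full AE collection starts with the first dose.

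**The concern.** The two documents define the same safety quantity differently, and the SAP is the narrower. Suppose an event begins in Washout or Screening, is recorded as an AE, is still present on Day 1 and becomes more severe on study drug. Operations Manual 4.2 counts it. SAP 9.2.1, read literally, does not, because its onset precedes the first dose.

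Such records can exist. Washout may last up to 10 months and Screening about 1.5 to 2.5 months. In that time subjects may stop hormonal therapy and undergo endometrial biopsy and saline infusion sonohysterography. At stake are the completeness of the TEAE tables and whether two analysts, each following one of the governing documents, would report the same counts.

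**Working it through.** The main check is a comparison of text. The plan gives no figure to reproduce.

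**Step 1: the definitions, element by element.**
- Start: after initiation of study drug (Operations Manual 4.2); after the first dose, with same-day onset included (SAP 9.2.1). No material difference.
- End: 30 days after the last dose (Operations Manual 4.2); onset no more than 30 days after discontinuation (SAP 9.2.1). These agree.
- Qualifying change: begins or worsens (Operations Manual 4.2); begins (SAP 9.2.1). These differ.

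**Step 2: does another SAP rule restore worsening?**
- The same-day rule still works on the onset date.
- The highest-severity rule in SAP 9.2 and 9.2.3 chooses which severity to report when an event occurs more than once. It does not make a pre-dose event treatment-emergent.
- SAP 9.2.2 to 9.2.5 contain no worsening clause.
- The version history in SAP 12.0 does not list the difference as a change, and neither document explains it.

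**Step 3: which outputs inherit the rule?**
- Inherit it: the treatment-emergent lines of the overview (9.2.2); the tables by SOC and PT, severity and relationship (9.2.3); and the treatment-emergent SAE summary (9.2.4).
- Not worded as limited to treatment-emergent events: all deaths (9.2.2 and the listing in 9.2.4) and the AESI summaries (9.2.5).

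**Step 4: which events are exposed?** An event must meet all of these conditions: it is an SAE or a protocol-related nonserious AE with onset before dosing; it is ongoing at first dose; it becomes more severe within the window; and the increase is not entered as a new AE with a post-dose onset. The documents give no number for this set.

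**Step 5: scale of one subject.** Planned arm sizes are 32 on elagolix and 16 on placebo (Protocol 7.7). Assume that all randomized subjects are dosed and analysed as randomized.
- Elagolix row: 1/32 = 0.031, or 3.1 percentage points.
- Placebo row: 1/16 = 0.0625, or 6.3 points.
- Omitting one elagolix subject lowers the elagolix-minus-placebo difference by 3.1 points. Omitting one placebo subject raises it by 6.3 points. The sign depends on the arm in which the omission falls.
- A row changes only if the subject is not already counted in it. The any-TEAE row changes only if she has no other TEAE.

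**The case against.** The strongest reply is that the difference in wording may have no practical effect. Before dosing, only serious and protocol-related nonserious events are recorded as AEs. Entry criteria 13 and 26 (Protocol 5.1) exclude clinically significant laboratory abnormalities other than disease-related ones, unstable conditions, and newly diagnosed conditions not stabilized before Day 1. Pre-existing conditions are recorded as medical history (Operations Manual 3.3 and 3.4). If one deteriorates on drug and is reported as an AE, it would ordinarily carry a post-dose onset and satisfy the SAP as written. The AE tables involve no planned hypothesis test, and this version of the protocol describes the study as exploratory. Protocol 7.4 also leaves the detail of safety analyses to the SAP.

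Most of this stands, and it limits the size of the problem. It does not remove the contradiction. Leaving detail to the SAP permits elaboration; it does not explain narrowing a definition that the protocol already states. The claim that a worsening will get its own onset date is an inference. The only explicit rule on deterioration, "then the deterioration of the condition for which the elective surgery/procedure is being done will be considered an AE", applies to pre-planned elective surgery or procedures.

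A reader might go further and infer that AESI counts are too low, that every safety table is affected, or that the two documents must give different counts. The text does not support this. The AESI summaries and all deaths are not tied to SAP 9.2.1, and the counts agree if no such event occurs or if each worsening is entered as a new AE.

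**Conclusion.** The inconsistency is real and the severity is minor. For any row built on SAP 9.2.1, the SAP rule can only match or fall below the protocol rule within an arm. The number of subjects affected is unknown, probably very small and possibly zero. It depends on a recording convention that the documents do not state.

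It would be tempting to conclude that the SAP makes elagolix look safer. That does not follow: an omission on placebo would have the opposite effect, and nothing indicates which arm would lose events. The primary efficacy analysis is not touched.

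**What to change.** Before database lock:
1. Amend SAP 9.2.1 so that a treatment-emergent AE is one whose onset or increase in severity falls after the first dose and no later than 30 days after the last dose.
2. Keep the existing same-day onset rule.
3. State that an increase in severity of a pre-dose AE is identified either by a new AE record with its own onset date or by a dated severity change on the existing record. Without one of these, worsening cannot be programmed: Protocol 6.1 asks for a severity rating of each AE but does not say that changes are dated.

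The cost is a short SAP amendment, a small amount of programming, and some data-recording work if dated severity changes are not already captured.

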### **9.2.2 Adverse Event Overview**

An overview of treatment-emergent AEs will be presented consisting of the number and percentage of subjects experiencing at least one event for each of the following AE categories:

- Any treatment-emergent AE
- Any treatment-emergent AE related to study drug according to the investigator
- Any severe treatment-emergent AE
- Any serious treatment-emergent AE
- Any treatment-emergent AE leading to discontinuation of study drug
- Any treatment-emergent AE leading to death
- All deaths

### **9.2.3 Treatment-Emergent Adverse Events by SOC and/or PT**

Treatment-emergent adverse events will be summarized by SOC and PT; by maximum relationship to study drug as assessed by the investigator (e.g., reasonable possibility or no reasonable possibility) and SOC and PT; by maximum severity and SOC and PT; and by subject number and SOC and PT. Specific adverse events will be counted once for each subject for calculating percentages, unless stated otherwise. In addition, if the same adverse event occurs multiple times within a subject, the highest severity and level of relationship to investigational product will be reported.

When summarizing AEs by relationship or severity, if a subject has an event with unknown severity or relationship then the subject will be counted in the severity/relationship category of "unknown" even if the subject has a second occurrence of the same event with a severity/relationship present. The only exception is if the subject has a second occurrence of the same event with the most extreme severity (i.e., "severe") or the most extreme relationship category (i.e., "reasonable possibility"). In this case, the subject will be counted under these most extreme severity/relationship categories.

In addition, treatment-emergent adverse events will be summarized by PT and sorted by decreasing frequency for the elagolix treatment group.

#### **9.2.4 SAEs (Including Deaths) and Adverse Events Leading to Study Drug Discontinuation**

Treatment-emergent SAEs (including deaths) and AEs leading to study drug discontinuation will be summarized by SOC and PT and in listing format.

A listing of all deaths will be generated.

#### **9.2.5 Adverse Events of Special Interest**

Adverse events of special interest will be summarized by SOC and PT and will be based on standardized or company MedDRA queries (SMQs, CMQs, or PMQs). Adverse events of special interest are listed in [Appendix B](#).

### **9.3 Analysis of Laboratory Data**

Data collected from central and local laboratories, including additional laboratory testing due to an SAE, will be used in all analyses, except for Baseline where SAE-related laboratory assessments on or before the first dose of study drug will be excluded. The clinical laboratory tests defined in the protocol operations manual (e.g., hematology and clinical chemistry) will be summarized.

Each laboratory variable will be summarized for all time points (starting with Baseline) with the number of non-missing observations, mean and standard deviation, median, minimum and maximum.

#### **Laboratory Data in the Treatment Period**

Mean change from baseline to each applicable post-baseline visit will be summarized for selected laboratory variables, with the number of observations, baseline mean, and visit mean. The change from baseline mean, standard error, and 95% confidence interval will be presented for the mean change from baseline within each treatment group and difference between treatment groups (elagolix vs. placebo). The selected laboratory variables include the following: lipid variables, liver variables (alkaline phosphatase,

ALT, AST, bilirubin), glucose, hemoglobin, hematocrit, platelet count, and Red Blood Cell (RBC) count. For lipid variables, in addition to low-density lipoprotein cholesterol (LDL-C), high-density lipoprotein cholesterol (HDL-C), total cholesterol, and triglycerides (TG), the following ratios will be included: the ratio of total cholesterol to HDL-C, the ratio of LDL-C to HDL-C, the ratio of TG to HDL-C, and the ratio of non-HDL-C (calculated as total cholesterol minus HDL-C) to HDL-C.

Changes in selected laboratory parameters will be tabulated using shift tables either by NCI CTC criteria or categorized as low, normal, or high based on the normal ranges of the laboratory used for each sample. For those analytes that are not reflected in the NCI CTC criteria, exceptions to standard CTC lab grading criteria for elagolix studies will be used as specified in [Appendix C](#). A shift table from baseline either to the worse value (based on NCI CTC criteria) during treatment or to minimum and maximum value (based on normal range), will be created. A similar shift table will be provided to summarize shifts from baseline to the final post-baseline value.

Laboratory abnormalities meeting CTC criteria grade 3 and 4 will be summarized.

The number and percentage of subjects meeting the following criteria will be summarized at Baseline and each applicable visit by treatment group in the Treatment Period:

- Total cholesterol:  $\leq 300$ ,  $> 300 - \leq 400$ ,  $> 400 - \leq 500$ , and  $> 500$  mg/dL
- HDL-C:  $< 40$  and  $\geq 40$  mg/dL
- LDL-C:  $< 130$ ,  $\geq 130 - < 160$ ,  $\geq 160 - < 190$ , and  $\geq 190$  mg/dL
- TG:  $\leq 150$ ,  $> 150 - \leq 300$ ,  $> 300 - \leq 500$ ,  $> 500 - \leq 1000$ , and  $> 1000$  mg/dL
- LDL-C/HDL-C ratio:  $\leq 3$ , and  $> 3$
- Total cholesterol/HDL-C ratio:  $\leq 4.5$ , and  $> 4.5$ .

Laboratory abnormalities will be evaluated based on Potentially Clinically Important (PCI) criteria as below. For each laboratory PCI criterion, the number and percentage of subjects who have a laboratory value meeting the criteria will be summarized by treatment

group. Listings will be provided to summarize subject-level laboratory data for subjects meeting PCI criteria.

The PCI criteria for lipid parameters during the Treatment Period are:

- Total cholesterol > 200 mg/dL
- LDL-C > 130 mg/dL
- LDL-C > 160 mg/dL
- HDL-C < 40 mg/dL
- TG > 150 mg/dL
- TG/HDL-C ratio > 3.5
- LDL-C/HDL-C ratio > 4.

Plots will be provided by treatment group for HDL-C, LDL-C, triglycerides, and hemoglobin during the Treatment Period:

- Final post-baseline lab values vs. Baseline lab values;
- Final post-baseline lab values vs. Baseline lab values for subjects with NCI CTC Grade 3 or 4;
- Worst post-baseline lab values vs. Baseline lab values;
- Worst post-baseline lab values vs. Baseline lab values for subjects with NCI CTC Grade 3 or 4

Plots will be provided by treatment group for HDL-C, LDL-C, and triglycerides during the Treatment Period:

- Mean percent change from Baseline in lipid parameters over time.

Plots of mean lab values over time during the Treatment Period will be provided for hemoglobin, total cholesterol, HDL-C, LDL-C, triglycerides (TG), LDL-C/HDL-C ratio, ALT, AST, bilirubin, apolipoprotein A and B.

Listings of subjects with at least one ALT/AST assessment meeting CTC grade 3 or 4 during the Treatment Period, subjects with at least one HDL C/LDL-C/TG/total cholesterol assessment meeting CTC grade 3 or 4 during the Treatment Period will be provided.

